Long-term opioid therapy became a mainstay of chronic pain management over the past two decades, despite a lack of evidence for effectiveness. Now, in response to evidence that opioid therapy is associated with serious dose-related harms, clinicians and health systems are challenged to achieve a patient-centered shift in pain management from over-reliance on long-term opioid therapy to more effective use of evidence-based pain treatment approaches. Clinicians and health care decision-makers face gaps in evidence however for how to achieve these goals. Our approach is informed by patient partners who emphasized the primary need for individualized pain care and support to achieve improved pain outcomes. Accordingly, our central focus is on optimizing pain care, which we see as the first and most important step toward patient-centered opioid dose reduction.

Study aims

The overall objective of this research is to improve effectiveness and safety of pain management among patients with chronic pain. This 12-month pragmatic randomized trial will compare two pain care delivery strategies, which differ substantially in comprehensiveness and resource intensity, to improve pain and reduce opioid use among Veterans. We will also conduct an opioid tapering strategy substudy that will examine comparative effectiveness of tapering with or without the option for buprenorphine rotation in the high-dose subgroup of study participants.

Aim 1: To compare telecare collaborative pain management versus integrated pain team management for improving pain and reducing opioid use in VA patients on long-term moderate to high-dose opioids for chronic pain.

Aim 2: To compare standard taper options versus expanded taper options for improving pain and reducing opioid use among VA patients on long-term high-dose opioids for chronic pain.

Secondary Aim: To understand patients' and clinicians' experiences with the study interventions and identify strategies to enhance future implementation and dissemination of effective pain care interventions.

Study design

This is a pragmatic comparative effectiveness trial at ten VA sites to compare two distinct interventions augmenting primary care management of chronic pain for patients on long-term opioid therapy. Randomization at the individual patient level will assign patient participants to either 1) telecare collaborative management (TCM) or 2) integrated pain team (IPT) management arms for 12 months. In both arms, patients receive pain care and opioid taper planning tailored to preferences and adjusted as needed to achieve individualized treatment goals. Among participants in a high-dose subgroup, the opioid taper strategy substudy will examine comparative effectiveness of tapering with or without the option for buprenorphine rotation.

Intervention and comparators

The TCM arm uses a medication management approach delivered by a clinical pharmacist care manager in collaboration with a consulting physician to address common barriers to effective

pain medication management in primary care. The IPT arm uses a biopsychosocial management approach delivered by an interdisciplinary team and emphasizes multimodal pain management and behavioral activation. For participants who agree to opioid dose reduction or discontinuation, opioid tapering will be conducted in both arms. Participants receiving moderate-doses (20-69 ME mg/day) will receive standard taper options, which incorporate shared decision-making to guide medication selection and rate of dose changes. Patients on high-dose opioids (≥ 70 ME mg/day) will be randomized to standard options or expanded options. The expanded options arm differs from standard options only in that it includes the additional option of buprenorphine rotation.

Study population

VA primary care patients receiving long-term moderate to high-dose opioid therapy for chronic pain of at least moderate severity will be eligible. Long-term is ≥ 90 consecutive days. Moderate to high dose is ≥ 20 morphine-equivalent (ME) mg/day. For subgroup definition, high-dose is ≥ 70 ME mg/day. Exclusion criteria are cognitive impairment; unstable or severe untreated psychiatric disorder; severe unstable or end-stage medical disease; suspected controlled substance diversion; and inability to communicate by telephone.

Outcomes

The primary study outcome is pain response at 12 months, defined as a 30% improvement in the Brief Pain Inventory (BPI). The main opioid dose outcome is 50% reduction in opioid daily dose. The main composite outcome is the proportion with 30% improvement in pain and 50% decrease in opioid daily dose, representing dual improvements in pain and opioid safety. We will assess secondary patient-relevant outcomes including function, quality of life, symptoms (e.g., depression, anxiety, sleep, fatigue), and adverse effects.

Analytic methods

All participants will be assessed in the arms to which they are assigned. An estimated sample size of 970 patients from 10 sites provides 80% power for a 2-sided chi-squared test comparing pain response rates for TCM and IPT if IPT adds 10% to the response rate, and $> 85\%$ power if IPT adds 11% to the response rate. We will use all follow-up data in repeated-measures logistic regression modeling 30% reduction from baseline in BPI scores. For the second aim, we estimate 80% power power to detect small to moderate effects (Cohen d or standardized difference) in mean BPI scores of 0.35 or more.

We will evaluate heterogeneity of treatment effects in 5 pre-specified subgroups that may be differentially responsive to treatment, at greater risk for opioid harms, or more likely to have difficulty reducing opioids (patients treated with high-dose opioids and those with depression symptoms, post-traumatic stress symptoms, potential substance use disorder (SUD), and fibromyalgia symptoms). We will use repeated-measures linear regression to examine interactions of subgroup with treatment assignment.

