1. STUDY OBJECTIVES

1.1 Primary Objectives

1.1.1 Aim 1

Aim 1 is to compare telecare collaborative pain management (TCM) versus integrated pain team (IPT) management for improving pain and reducing opioid use in VA patients on long-term moderate to high-dose opioids for chronic pain.

All participants will be randomized to one of two care management approaches: 1) TCM or 2) IPT. To assess improvement in pain and reduction in opioid use, we will compare TCM versus IPT groups on three main outcomes. First, the primary outcome is pain response, defined as a 30% improvement in Brief Pain Inventory (BPI) total score from baseline to the final study outcome assessment at 12 months. Our second main outcome is opioid daily dose reduction of 50% from baseline to 12 months, based on VA pharmacy dispensing data. The main composite outcome is the proportion with both a pain response and opioid dose reduction, representing dual improvements in pain and regimen safety.

1.1.2 Aim 2

Aim 2 is to compare standard versus expanded taper options for improving pain and reducing opioid use among patients on high-dose opioid therapy at baseline.

Participants in the high-dose therapy subgroup will be randomized to receive one of two opioid taper arms: a) standard options or b) expanded options, which includes the additional option of buprenorphine rotation. To assess the primary outcome of pain severity, we will compare standard versus expanded options groups on mean BPI total scores. Between-group differences in opioid daily dose and the composite pain response and opioid dose reduction outcome will also be examined. We hypothesize that offering the option of buprenorphine rotation will improve BPI scores and reduce opioid daily dose.

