7.1.2 Subgroup power estimates

A difference of 1 unit in BPI is considered clinically significant and the SD of the BPI scores is typically about 2 units. A sample size of 776 participants at the 12-month

assessment will provide $> 80\%$ power for detecting a clinically meaningful difference in intervention effects across subgroups with prevalence of at least 40%, assuming a Bonferroni corrected significance level of 0.01. For a 1.2-unit difference in intervention effects, the study will have $> 85\%$ power for subgroup prevalence of 25% or more. Within a subgroup, the study will have $> 80\%$ power to detect an intervention effect of 1 unit or more for subgroup prevalence of $> 25\%$ and a 0.01 significance level. These power calculations for comparisons of 12-month outcomes consider just the data for this assessment point as a worst-case scenario. The repeated measures analyses discussed below should have power greater than discussed here for comparing the 12-month outcomes. Based on preliminary data, we anticipate the proposed sample size will provide adequate power for planned assessments of the HTE for all planned subgroups; if prevalence of any subgroup is $< 25\%$, assessment of HTE across subgroups will be exploratory.

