7.4 Pre-Specified Subgroup Analyses

We will examine variation in the intervention effects on the change in BPI within clinical subgroups defined by presence or absence at baseline of the subgroup status/conditions described above. For each subgroup measure, we will fit a repeated-measures linear regression modelling change from baseline in BPI at the quarterly follow-up assessments using assigned intervention, assessment point, subgroup indicator and all interactions between these three measures together with baseline BPI score and its interaction with assessment point as explanatory measures. Assessment points will be incorporated as random effects, with an unstructured covariance, to model potential correlation among outcomes for individuals. Our primary assessment of an interaction between intervention and the subgroup measure will use the model-based two-sided Wald test for an interaction at the 12-month assessment, using a 0.005 significance level. Weighted selection model analyses similar to those described above will examine sensitivity of 12-month results to response biases.

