7.7 Analysis of Adverse Events

Information about hospitalizations, ED visits, SUD admissions, and other adverse events will be extracted from VA administrative data. We will compare intervention arms with respect to the 1) proportion of individuals reporting any hospitalization, ED visit, and SUD admission and 2) number of hospitalization, ED visit, or SUD admissions per person at a) each assessment time-point and b) overall using, respectively, Pearson chi-square tests and, given the reasonable large sample in each arm, large sample normal approximation based z-tests. Similar comparisons will be made between other adverse events. We will also break these comparisons out by baseline dosage and assignment to the expanded taper options arm.

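### The five subgroups are justified partly by opioid harm and difficulty reducing opioids, yet the only specified subgroup-by-arm analysis is on BPI change; none is pre-specified for dose reduction or the composite

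*Combined protocol and SAP*

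**What the plan says.** The Study Abstract (Analytic methods) describes "5 pre-specified subgroups that may be differentially responsive to treatment, at greater risk for opioid harms, or more likely to have difficulty reducing opioids": high-dose opioid therapy, depression symptoms, post-traumatic stress symptoms, potential SUD and fibromyalgia symptoms. Section 1.2.1 lists the same five and expects IPT to be superior in all but fibromyalgia, without naming the outcome.

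Section 1.1.1 gives Aim 1 three main outcomes. Pain response is primary. Then: "Our second main outcome is opioid daily dose reduction of 50% from baseline to 12 months, based on VA pharmacy dispensing data". The third is the composite of the two. Section 7.3 analyses the dose and composite outcomes by arm, with no subgroup term.

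Section 7.4 is specific about outcome: "We will examine variation in the intervention effects on the change in BPI within clinical subgroups defined by presence or absence at baseline". Its test is a "two-sided Wald test for an interaction at the 12-month assessment, using a 0.005 significance level". Section 7.1.2 gives subgroup power on the BPI scale only: "A difference of 1 unit in BPI is considered clinically significant and the SD of the BPI scores is typically about 2 units".

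Three other places touch the question:
- Sections 1.2.3 and 7.5 promise variation by sex, site and enrollment time, and moderation by covariates that are not listed.
- Section 7.6 refits the preceding analyses in high-dose participants, with taper assignment entered alongside TCM/IPT.
- Section 7.7, on adverse events, adds: "We will also break these comparisons out by baseline dosage and assignment to the expanded taper options arm".

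**The concern.** Of the three reasons given for choosing the subgroups, two concern opioids: risk of harm and difficulty cutting the dose. The specified analysis addresses differential response in pain. Aim 1 asks about both pain and opioid use, and Section 2.2 says clinical leaders need evidence on both goals. Followed as written, the plan tests heterogeneity on the pain half and leaves the opioid half almost wholly to an overall arm comparison.

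An overall comparison can hide opposite effects. As an illustration only: with subgroup prevalence 40%, an IPT-minus-TCM difference in dose reduction of +12 points inside the subgroup and -8 outside averages to 0.4 × 12 - 0.6 × 8 = 0, so a 20-point interaction would not show. Nothing in the documents suggests that this pattern is likely. The practical risk is that subgroup findings on opioid dose, if they appear, will have been chosen after the data were seen.

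**Working it through.** **1. What is specified for each subgroup**

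| TCM versus IPT analysis | High dose | Depression, post-traumatic stress, SUD, fibromyalgia |
|---|---|---|
| Interaction, BPI change | Yes (7.4) | Yes (7.4) |
| Interaction, 50% dose reduction | No | No |
| Interaction, composite | No | No |
| Within-subgroup dose estimate | Implied (7.6) | No |
| Adverse events by subgroup | Yes, by baseline dosage (7.7) | No |

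Section 7.6 counts as implied because the analyses it modifies include the dose and composite models of Section 7.3. It yields an estimate inside the high-dose group, with no moderate-dose counterpart and no interaction.

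**2. The plan's own subgroup power**

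Inputs: N = 776 (Section 7.1); SD 2, differences of 1 and 1.2 units, prevalences q of 40% and 25%, alpha 0.01 (Section 7.1.2); 1:1 allocation (Section 4.3.9).

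SE = SD × sqrt(4/(Nq) + 4/(N(1-q))); power = Φ(d/SE - z), with z = 2.576 at alpha 0.01.

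- 1 unit, q = 40%: SE = 2 × sqrt(4/310.4 + 4/465.6) = 0.293; power 79.8% (stated: above 80%).
- 1.2 units, q = 25%: SE = 0.332; power 85.1% (stated: above 85%).
- 1 unit within a subgroup, q = 25%: SE = 2 × sqrt(4/194) = 0.287; power 81.8% (stated: above 80%).

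The figures reproduce to within rounding. Section 7.1.2 refers to "effects across subgroups with prevalence of at least 40%, assuming a Bonferroni corrected significance level of 0.01", whereas Section 7.4 tests at 0.005. At 0.005 the two interaction powers fall to 72.7% and 79.2%. The two levels need reconciling before any new analysis borrows one.

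**3. What the dose outcome could support**

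The same formula applies with SD = sqrt(p(1-p)), so SE = sqrt(4p(1-p)/(Nq(1-q))). The rate p = 30% is an assumption. Prevalence 35% is the high-dose share in Section 7.1.1; 25% and 40% come from Section 7.1.2. N = 970 is an upper bound that assumes complete dispensing data; N = 776 is the planning figure. Example: N = 970, q = 25% gives sqrt(0.84/181.9) = 0.068.

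| N | q | SE | 95% CI half-width (points) | Power for 20 points at 0.005 | Detectable with 80% power at 0.01 / 0.005 (points) |
|---|---|---|---|---|---|
| 970 | 25% | 0.068 | 13.3 | 55% | 23 / 25 |
| 970 | 35% | 0.062 | 12.1 | 67% | 21 / 22 |
| 970 | 40% | 0.060 | 11.8 | 70% | 21 / 22 |
| 776 | 25% | 0.076 | 14.9 | 43% | 26 / 28 |
| 776 | 35% | 0.069 | 13.5 | 54% | 24 / 25 |
| 776 | 40% | 0.067 | 13.2 | 57% | 23 / 25 |

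Across assumed rates of 20% to 50%, the interaction detectable at 0.01 is 18 to 25 points at N = 970 and 20 to 28 points at N = 776. Because p(1-p) is symmetric about 50%, this also covers rates up to 70%, the top of the range that Section 7.5 considers for the standard options arm. Power for 20 points at 0.005 is 46% to 84% (N = 970) or 35% to 73% (N = 776). A 10-point interaction at 0.005, with p = 30% and N = 970, has 9% to 13% power.

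**The case against.** The best defence is that this is a deliberate choice. BPI response is the primary outcome, the protocol puts pain care first (Abstract, Section 2.2), and the abstract's reference to linear regression for the subgroups agrees with Section 7.4. Confining confirmatory heterogeneity tests to the primary outcome's scale, at a corrected alpha, is sound practice. The abstract joins its reasons with an or and commits to no outcome for each. All this stands as an argument against adding confirmatory tests. It does not explain why two of three main outcomes have no pre-specified subgroup estimates at all.

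A second defence is that the moderation sentence in Section 7.5 closes a section that opens with dose outcomes. But it names none of the subgroup conditions apart from sex, site and time, and it refers back to methods that are BPI models. It leaves room for such analyses without specifying one.

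A reader might infer that the trial cannot say which care model reduces opioids better in these patients. The documents do not support that: baseline subgroup status and dispensing data are both collected (Sections 6.2 and 6.3.2). Nor would the reader learn nothing about high-dose patients, given Sections 7.6 and 7.7. The opposite overstatement, that the data comfortably support a formal interaction test, fails on the power figures above. VA dispensing data also miss outside medicines, which Section 7.2 acknowledges as an issue.

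**Conclusion.** The point holds in a limited form. No subgroup-by-arm interaction is pre-specified for 50% dose reduction or the composite in any of the five subgroups. In four of them no within-subgroup dose or adverse-event comparison is specified either. Any such result would be post hoc; it would not be impossible to obtain. The primary conclusion of the trial is unaffected.

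Precision is modest: interaction intervals of about 12 to 15 points either side at an assumed 30% rate, and roughly 20 points or more needed for detection. That supports pre-specified estimation and does not support confirmatory testing. The figures rest on the assumed rate, on prevalences of 25% to 40% (only the high-dose share is given in the plan), on equal allocation within subgroups, and on N between 776 and 970. The composite needs the 12-month BPI, so the lower N is the safer guide for it.

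**What to change.** In Section 7.4, keep the 12-month BPI interaction as the main heterogeneity test. Add, for each of the five subgroups:

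- the 12-month IPT-minus-TCM difference in the proportion with 50% dose reduction, inside and outside the subgroup, and the interaction estimate, each with a confidence interval;
- the same for the composite.

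Label these as exploratory estimation, and state that only interactions of roughly 20 points or more are detectable, so that an interval including zero is not read as absence of heterogeneity. In Section 7.7, summarize hospitalizations, ED visits and SUD admissions by arm within the same five subgroups, descriptively. Reconcile the 0.01 in Section 7.1.2 with the 0.005 in Section 7.4.

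The cost is SAP wording and about ten extra models (five subgroups × two outcomes) on data already planned. The downside is more exploratory comparisons, which the labelling is meant to contain.

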1. STUDY OBJECTIVES

1.1 Primary Objectives

1.1.1 Aim 1

Aim 1 is to compare telecare collaborative pain management (TCM) versus integrated pain team (IPT) management for improving pain and reducing opioid use in VA patients on long-term moderate to high-dose opioids for chronic pain.

All participants will be randomized to one of two care management approaches: 1) TCM or 2) IPT. To assess improvement in pain and reduction in opioid use, we will compare TCM versus IPT groups on three main outcomes. First, the primary outcome is pain response, defined as a 30% improvement in Brief Pain Inventory (BPI) total score from baseline to the final study outcome assessment at 12 months. Our second main outcome is opioid daily dose reduction of 50% from baseline to 12 months, based on VA pharmacy dispensing data. The main composite outcome is the proportion with both a pain response and opioid dose reduction, representing dual improvements in pain and regimen safety.

1.1.2 Aim 2

Aim 2 is to compare standard versus expanded taper options for improving pain and reducing opioid use among patients on high-dose opioid therapy at baseline.

Participants in the high-dose therapy subgroup will be randomized to receive one of two opioid taper arms: a) standard options or b) expanded options, which includes the additional option of buprenorphine rotation. To assess the primary outcome of pain severity, we will compare standard versus expanded options groups on mean BPI total scores. Between-group differences in opioid daily dose and the composite pain response and opioid dose reduction outcome will also be examined. We hypothesize that offering the option of buprenorphine rotation will improve BPI scores and reduce opioid daily dose.

1.2 Secondary Objectives

1.2.1 Subgroup analyses

We will examine differential response to TCM and IPT among subgroups of study participants. Subgroups are not mutually exclusive and are defined as presence (yes/no) of the following characteristics at baseline:

- High-dose opioid therapy (≥ 70 ME mg/day)
- Depression symptoms
- Post-traumatic stress symptoms
- Potential SUD
- Fibromyalgia symptoms

We hypothesize that IPT will be superior to TCM in the following subgroups: high-dose opioid therapy, depression, post-traumatic stress, and SUD.

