7.5 Secondary Analyses and Analysis of Secondary Outcomes

If the proportion of patients in the standard options arm achieving the 50% dose reduction outcome falls in the range 20%-70%, the anticipated sample size will provide 80% power to detect between-group differences in the range of 14 and 17%. The study will have this same level of power for comparable differences in the proportions achieving a 25% dose reduction and proportions with any dose reduction. We will have 80% power for assessing small to moderate differences of 0.35 SD in mean dose change.

The secondary dose escalation outcome is defined as a proportional increase in daily dose of $\geq 25\%$ from baseline to 12 months. If 5-15% of participants meet this dose escalation outcome, we will have 80% power to detect between-group differences of 7-8%.

In addition, we will assess between-group differences in the pain-related function, pain intensity, quality of life, fatigue and sleep, mental health measures, and physical symptoms over the follow-up period. We will fit separate repeated-measures linear regressions modelling change from baseline at the follow-up assessments using assigned intervention, assessment point and their interaction together with the respective baseline score and its interaction with assessment point as explanatory measures. Assessment points will be incorporated as random effects, with an unstructured covariance, to model potential correlation among outcomes for individuals. The primary assessment of an intervention effect on a particular outcome will use the model based 2-sided Wald test for a difference at the 12-month assessment together with the point and confidence interval estimates for the mean difference in change from baseline.

We will examine variation in effects by sex, study site and over the course of enrollment, as well as moderation of effects by relevant covariates. Analyses will be similar to the subgroup analyses described above.

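### Depression and post-traumatic stress are tested as effect modifiers only in yes/no form; a companion score-by-arm interaction in Section 7.4 would guard against missing graded moderation

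*Combined protocol and SAP*

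**What the plan says.** Section 1.2.1 lists five baseline subgroups: high-dose opioid therapy, depression symptoms, post-traumatic stress symptoms, potential SUD and fibromyalgia symptoms. It codes all of them the same way: "Subgroups are not mutually exclusive and are defined as presence (yes/no) of the following characteristics at baseline". It hypothesises that IPT is superior in the first four.

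Section 7.4 carries the coding into the analysis: "We will examine variation in the intervention effects on the change in BPI within clinical subgroups defined by presence or absence at baseline". The primary heterogeneity test is the "model-based two-sided Wald test for an interaction at the 12-month assessment, using a 0.005 significance level".

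Section 6.2.3 (Table 2) schedules mood, including depression and PTSD, at baseline and says that patient-reported measures are validated. Section 7.5 models change in the mental health measures "together with the respective baseline score and its interaction with assessment point as explanatory measures". Baseline mental health scores are thus already used as covariates in models of their own change.

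Section 7.1.2 gives the subgroup power: 776 participants, SD 2, "assuming a Bonferroni corrected significance level of 0.01". For the effect size it says: "A difference of 1 unit in BPI is considered clinically significant". If a subgroup has prevalence below 25%, "assessment of HTE across subgroups will be exploratory".

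No instrument or cut-off is given for any symptom subgroup. Sections 1.2.3 and 7.5 also promise to look at moderation by covariates that they do not name.

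**The concern.** Depression and post-traumatic stress symptoms vary in degree. If the IPT advantage grows gradually with severity, a two-level indicator treats patients just above and far above the cut alike, and the interaction test loses information. These tests are already demanding: they are interactions, at a strict level, in a trial sized for a main effect. What is at stake is the chance of detecting graded moderation for two characteristics on which the plan states a directional hypothesis. The primary comparison of TCM and IPT is not affected.

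The yes/no form also makes the status of a test depend on where the cut is placed, because prevalence below 25% makes that assessment exploratory. A test on the score does not depend on that cut.

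**Working it through.** **Inputs from the documents.** N = 776 at 12 months (80% of 970, Section 7.1). SD 2, interaction 1 unit (1.2 units in the second scenario), prevalence p of 40% and 25%, alpha 0.01 (Section 7.1.2). Planned test level 0.005 (Section 7.4). Equal allocation to TCM and IPT in both dose strata (Section 4.3.9).

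**Assumptions not in the documents.** A normally distributed score and linear moderation, unless stated otherwise.

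**1. The plan's own power.** For a yes/no moderator, SE = 2 x SD / sqrt(N p(1-p)), and power = Phi(delta/SE - critical value).
- p = 0.40, 1 unit: z = sqrt(776 x 0.24)/4 = 3.412. At alpha 0.01, Phi(3.412 - 2.576) = 79.8% (stated: above 80%).
- p = 0.25, 1.2 units: z = 1.2 x sqrt(776 x 0.1875)/4 = 1.2 x 3.016 = 3.619. Phi(3.619 - 2.576) = 85.1% (stated: above 85%).

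The stated figures reproduce to rounding.

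**2. Information lost by the cut.** With c the cut on a standard normal score, the relative efficiency of yes/no to score is phi(c)^2 / (p(1-p)).
- p = 0.40: 0.3863^2 / 0.24 = 0.622, a loss of 38%, as if N were 776 x 0.622 = 483.
- p = 0.25: 0.3178^2 / 0.1875 = 0.539, a loss of 46%, as if N were 776 x 0.539 = 418.

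For uniform, gamma, exponential, lognormal and bimodal scores at these prevalences, the loss runs from about 28% to 51%.

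**3. Power at the planned 0.005 (critical value 2.807), 1-unit interaction.** Under linear moderation the score test has z equal to the yes/no z divided by sqrt(relative efficiency): 3.412/sqrt(0.622) = 4.33 and 3.016/sqrt(0.539) = 4.11. Under a step exactly at the cut it is multiplied instead: 2.69 and 2.21.

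| Truth | Prevalence | Yes/no | Score |
|---|---|---|---|
| Linear | 40% | 72.7% | 93.6% |
| Linear | 25% | 58.3% | 90.4% |
| Step at the cut | 40% | 72.7% | 45% |
| Step at the cut | 25% | 58.3% | 28% |

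Simulation of the linear case (4,000 trials per setting) gives 71.9% v 93.4% at 40% and 56.2% v 90.2% at 25%.

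**4. Sensitivity to the size of the interaction.** At 1 unit the chance of a miss is 27.3% v 6.4% at 40% prevalence (4.2 times) and 41.7% v 9.6% at 25% (4.3 times). At 0.6 units the ratio is 1.3, and at 0.5 units 1.2. At 0.5 units and 40% prevalence, power is 13.5% v 26.0%, so both tests mostly miss.

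**5. Sensitivity to the worst-case inputs.** Take 95% completion (Section 7.2 reports more than this in similar studies), so N = 0.95 x 970 = 922, and assume a correlation of 0.5 between baseline and follow-up BPI, so residual SD = 2 x sqrt(0.75) = 1.73. Under linear moderation at 1 unit, power is 93% v 99.6% at 40% prevalence and 84% v 99% at 25%.

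**The case against.** **The yes/no form answers the stated question.** Section 1.2.1 hypothesises superiority within groups, and Section 7.1.2 powers within-group effects. A slope per score unit tests something different, and presence/absence is a legitimate way to report in a pragmatic trial. This stands, and with the step result above it rules out replacing the planned tests. A reader might infer that the score interaction should become the heterogeneity test; that would exchange one unverified shape assumption for another.

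**The loss is conditional.** A reader might take 38-46% as a property of this trial, or conclude that a real gradient would probably be reported as no heterogeneity. The documents support neither. They give no score distribution or cut-off, and at a 1-unit gradient the yes/no test still detects more often than it misses (73% and 58%).

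**High dose is different.** Opioid dose is a continuous 90-day mean (Section 6.3.2), so it is tempting to include it. But 70 ME mg/day is a randomisation stratum (Section 4.3.9) and determines who is randomised between taper options (Sections 1.1.2 and 3.1). The binary form has a design reason.

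**The source of the subgroups is not stated.** Section 6.3.1 also lists mental health diagnoses among the administrative data. That depression and post-traumatic stress status come from scores is a reasonable inference, not a documented fact. It does not defeat the point, because baseline measures of both are collected whichever source defines the indicator. For potential SUD, nothing shows a severity score behind it.

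**The plan may already allow it.** The covariate-moderation analyses in Sections 1.2.3 and 7.5 do not exclude continuous scores. They name none, however, and are described as resembling the subgroup analyses, so they are not a commitment.

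**Conclusion.** The point holds as a low-cost improvement for depression and post-traumatic stress, and for fibromyalgia if it is scored. It is not an error in the planned tests. The 21- and 32-point power differences at 40% and 25% prevalence rest on a roughly normal score, linear moderation, a 1-unit interaction and the plan's worst-case data. With baseline adjustment and high completion they fall to about 6 and 15 points, and under a step at the cut the advantage passes to the yes/no test. Since the shape of moderation is unknown, pre-specifying both forms is safer than relying on either alone.

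Two matters of error control go with this. Section 7.4 does not say which tests the 0.005 level covers, and Section 7.1.2 computes power at 0.01. At 0.005 the plan's own two scenarios give 72.7% and 79.2% instead of the stated figures above 80% and 85%.

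**What to change.** In Section 7.4:

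- Keep all five yes/no interaction tests as planned, including high dose.
- Name the instrument or data source and the cut-off for each symptom subgroup.
- Pre-specify, for depression and post-traumatic stress (and fibromyalgia if scored), a companion 12-month score-by-arm interaction on change in BPI, in the same repeated-measures model with the score in place of the indicator. Report the IPT-TCM difference at low, middle and high scores.
- State which tests share the 0.005 level, and reconcile it with the 0.01 in Section 7.1.2. If the family is the interaction tests alone, five tests use 5 x 0.005 = 2.5%, and two or three companions bring this to 3.5% or 4.0%. If five within-subgroup tests also belong at that level, ten tests already use 5% and the companions would exceed it, so the sponsor must define the family before adding them.

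The cost is SAP wording and two or three extra models, with no new data. The downsides are the additional tests and the linearity assumption in the companion model; keeping the yes/no tests covers a step at the cut.
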